5.4.3. Clinical laboratory evaluation

The following laboratory parameters are collected in the study as per protocol and will be presented in the SI units:

Table (5.4.3) 1 Gradable Laboratory Parameters

	Parameter	Worst highest	Worst lowest
Hematology	Hemoglobin	Hemoglobin increased	Anemia
	Eosinophils	Eosinophilia	NA
	Lymphocytes	Absolute lymphocytes count increased	Absolute lymphocytes count decreased
	Neutrophils	NA	Absolute neutrophils count decreased
	White blood cell (WBC) count	Leukocytosis	WBC decreased
	Platelet count	NA	Platelet count decreased
Serum chemistry	Alanine aminotransferase (ALT)	ALT increased	NA
	Albumin	NA	Hypoalbuminemia
	Alkaline phosphatase (ALP)	ALP increased	NA
	Aspartate aminotransferase (AST)	AST increased	NA
	Total bilirubin	Blood bilirubin increased	NA
	Gamma glutamyl transferase (GGT)	GGT increased	NA
	Calcium	Hypercalcemia	Hypocalcemia
	Serum creatinine	Creatinine increased	NA
	Glucose	Hyperglycemia	Hypoglycaemia
	Magnesium	Hypermagnesemia	Hypomagnesemia
Coagulation	Potassium	Hyperkalemia	Hypokalemia
	Sodium	Hypernatremia	Hyponatremia
	Activated Partial thromboplastin time (aPTT)	aPTT prolonged	NA
	International Normalized Ratio (INR)	INR increased	NA

Table (5.4.3) 2 Non Gradable Laboratory Parameters

	Parameter	Worst highest	Worst lowest
Hematology	Basophils	High basophils	Low basophils
	Hematocrit	High hematocrit	Low hematocrit
	Monocytes	High monocytes	Low monocytes
	Red blood cell (RBC) count	High RBC	Low RBC
Serum chemistry	Direct bilirubin	High direct bilirubin	Low direct bilirubin
	Indirect bilirubin	High indirect bilirubin	Low indirect bilirubin
	Blood urea nitrogen (BUN)	High BUN	Low BUN
	Carbon dioxide	High carbon dioxide	Low carbon dioxide
	Chloride	High chloride	Low chloride
	Phosphorus	High phosphorus	Low phosphorus
	Urea	High urea	Low urea
Coagulation	Prothrombin time (PT)	High PT	Low PT
Thyroid function tests	Free thyroxine	High free thyroxine	Low free thyroxine
	Thyroid stimulating hormone (TSH)	High TSH	Low TSH
	Triiodothyronine (T3) or free T3	High T3	Low T3

For serum chemistry, creatinine clearance will also be derived as per the Cockcroft-Gault formula:

$$\text{CrCl (mL/min)} = (140 - \text{Age(years)}) * [\text{Weight (kg)}] * (0.85 \text{ if Female}) / 72 * [\text{Serum creatinine (mg/dL)}]$$

For calcium, CTCAE grading is based on corrected calcium and ionized calcium. Corrected calcium is calculated from albumin and calcium as follows:

$$\text{Corrected calcium (mmol/L)} = \text{Total calcium (mmol/L)} + 0.02 * [40 - \text{Albumin (g/L)}]$$

Corrected calcium is derived based on calcium and albumin from the same date and visit. Lower reference range will be 2.1 mmol/L and upper reference range will be 2.6 mmol/L.

For laboratory tests covered by the NCI CTCAE v5.0, grades will be assigned for these tests as per [Appendix A](#). For laboratory tests not covered by the NCI CTCAE, results will be graded by the low/normal/high classifications based on laboratory normal ranges.

Listings will be generated separately for hematology, serum chemistry, coagulation and thyroid function laboratory tests.

A listing of pregnancy tests will also be provided.

5.4.4. Vital signs, clinical examination and other observations related to safety**5.4.4.1. Vital signs and clinical examination**

The following vital signs and clinical examination will be analysed:

- Weight (kg)
- BMI (kg/m²)
- Systolic Blood Pressure (SBP) (mmHg)
- Diastolic Blood Pressure (DBP) (mmHg)
- Heart Rate (b.p.m.)
- Respiratory Rate (breaths/minute)
- Temperature (°C)

They will be listed, in terms of value at baseline, value at each post-baseline visit under treatment as well as in terms of change from baseline to each post-baseline visit under treatment.

5.4.4.2. Electrocardiogram

The actual values and change from baseline over time will be presented for each electrocardiogram (ECG) parameter:

- Heart Rate (b.p.m.)
- PR interval (msec)
- QT interval (msec)
- Duration of QRS (msec)
- RR interval (msec)
- QTcF (msec) (Fridericia's correction). QTcF (msec) = [QT (msec)] / [RR interval (sec)]^{1/3} (values as per eCRF, not derived)

A listing will be provided. The listing will flag the maximum values and its maximum change from baseline.

5.4.4.3. ECOG-PS

ECOG-PS scores will be presented in a listing.

5.5. Quality of Life

Not applicable.

5.6. Pharmacokinetics analyses

Individual concentrations of ivosidenib (in plasma and tumor tissue), nivolumab and ipilimumab (in serum) for each visit and timepoint of collection by subject, will be presented as listings. Spaghetti plots of individual plasma concentration-time profiles for ivosidenib on Cycle 2 Day 1 will be plotted on linear-linear scale and log linear scales using nominal time.

CL1-95031-006 - Statistical Analysis Plan | VV-TMF-222226 | 1.0

S 095031CL1-95031-006 - Statistical Analysis Plan - Final version 1.0

Plots of concentrations of nivolumab and ipilimumab by visit may be presented based on available data. The Pharmacokinetic Analysis Set will be used for listings and figures of concentration data for ivosidenib, nivolumab and ipilimumab.

5.7. Pharmacodynamics analyses

Individual plasma and tumor 2-HG concentrations, at each visit and collection timepoint by subject will be listed. Spaghetti plots of individual 2-HG concentrations by visit may be plotted based on available data. The Pharmacodynamic Analysis Set will be the primary analysis set for listings and figures of 2-HG concentrations.

5.8. Immunogenicity analyses

A separate analysis plan will be developed on the immunogenicity analyses if needed.

5.9. Biomarkers analyses

A separate analysis plan will be developed on the biomarker analyses if needed.

6. INTERIM ANALYSIS

Since the study stopped enrollment after enrolling 7 patients for the Safety Lead-in phase and did not proceed to the Expansion phase, the futility interim analysis during the Expansion phase will not be conducted.

7. CHANGES TO PROTOCOL-PLANNED ANALYSES

Not applicable.

9. APPENDICES

9.1. Appendix A: Laboratory parameters toxicity grading

Following there's a list of study laboratory parameters with the corresponding rules for toxicity grade classification based on the NCI CTCAE v5.0. Reference ranges are used: lower limit of normal (LLN) and upper limit of normal (ULN).

In case there are several grades for the same record, choose the worst grade (i.e., grade with the highest number).

Table (A) 1 - Laboratory Parameters Toxicity Grading

Parameter (unit)	Grade	Low Grade	High Grade
Albumin (g/L)	Grade 0	\geq LLN	
	Grade 1	[30; LLN[
	Grade 2	[20; 30[
	Grade 3	<20	
	Grade 0		If baseline value normal or not available: \leq ULN If baseline value abnormal and post-baseline: <2.0*baseline
ALP (IU/L)	Grade 1		If baseline value normal or not available:]ULN; 2.5*ULN] If baseline value abnormal and post-baseline: [2.0*baseline; 2.5*baseline]
	Grade 2		If baseline value normal or not available:]2.5*ULN; 5.0*ULN] If baseline value abnormal and post-baseline: [2.5*baseline; 5.0*baseline]
	Grade 3		If baseline value normal or not available:]5.0*ULN ; 20.0*ULN] If baseline value abnormal and post-baseline:]5.0*baseline; 20.0*baseline]
	Grade 4		If baseline value normal or not available: > 20.0*ULN If baseline value abnormal and post-baseline: >20.0*baseline
	Grade 0		If baseline value normal or not available: \leq ULN If baseline value abnormal or post-baseline: <1.5*baseline
ALT (IU/L)	Grade 1		If baseline value normal or not available:]ULN; 3.0*ULN] If baseline value abnormal or post-baseline: [1.5*baseline; 3.0*baseline]
	Grade 2		If baseline value normal or not available:]3.0*ULN; 5.0*ULN] If baseline value abnormal or post-baseline: [3.0*baseline; 5.0*baseline]
	Grade 3		If baseline value normal or not available:]5.0*ULN; 20.0*ULN] If baseline value abnormal or post-baseline:]5.0*baseline; 20.0*baseline]
	Grade 4		If baseline value normal or not available: >20.0*ULN If baseline value abnormal or post-baseline: >20.0*baseline
	Grade 0		\leq ULN
aPTT (sec)	Grade 1]ULN; 1.5*ULN]
	Grade 2]1.5*ULN; 2.5*ULN]
	Grade 3		>2.5*ULN
	Grade 0		If baseline value normal or not available: \leq ULN If baseline value abnormal or post-baseline: <1.5*baseline
AST (IU/L)	Grade 1		If baseline value normal or not available:]ULN; 3.0*ULN]

CL1-95031-006 - Statistical Analysis Plan | VV-TMF-222226 | 1.0

S 095031

CL1-95031-006 - Statistical Analysis Plan - Final version 1.0

Parameter (unit)	Grade	Low Grade	High Grade
Corrected calcium (mmol/L)	Grade 2		If baseline value abnormal or post-baseline: [1.5*baseline; 3.0*baseline]
			If baseline value normal or not available:]3.0*ULN; 5.0*ULN] If baseline value abnormal or post-baseline:]3.0*baseline; 5.0*baseline]
			If baseline value normal or not available:]5.0*ULN; 20.0*ULN] If baseline value abnormal or post-baseline:]5.0*baseline; 20.0*baseline]
			If baseline value normal or not available: >20.0*ULN If baseline value abnormal or post-baseline: >20.0*baseline
	Grade 0	≥LLN	≤ULN
	Grade 1	[2.0; LLN[]ULN; 2.9]
	Grade 2	[1.75; 2.0[]2.9; 3.1]
	Grade 3	[1.5; 1.75[]3.1; 3.4]
	Grade 4	<1.5	>3.4
	Grade 0		≤ULN or If post-baseline: ≤baseline
	Grade 1		>ULN and If post-baseline: >baseline
GGT (IU/L)	Grade 0		If baseline value normal or not available: ≤ULN If baseline value abnormal or post-baseline: <2.0*baseline
	Grade 1		If baseline value normal or not available:]ULN; 2.5*ULN] If baseline value abnormal or post-baseline:]2.0*baseline; 2.5*baseline]
	Grade 2		If baseline value normal or not available:]2.5*ULN; 5.0*ULN] If baseline value abnormal or post-baseline:]2.5*baseline; 5.0*baseline]
	Grade 3		If baseline value normal or not available:]5.0*ULN; 20.0*ULN] If baseline value abnormal or post-baseline:]5.0*baseline; 20.0*baseline]
	Grade 4		If baseline value normal or not available: >20.0*ULN If baseline value abnormal: >20.0*baseline
Glucose (mmol/L)	Grade 0	≥LLN	If baseline available and >ULN: ≤baseline If baseline available and ≤ULN: ≤ULN If baseline not available: ≤ULN
	Grade 1	[3.0; LLN[If baseline available and >ULN: >baseline If baseline available and ≤ULN: >ULN If baseline not available: >ULN
	Grade 2	[2.2; 3.0[
	Grade 3	[1.7; 2.2[

CL1-95031-006 - Statistical Analysis Plan | VV-TMF-222226 | 1.0

S 095031

CL1-95031-006 - Statistical Analysis Plan - Final version 1.0

Parameter (unit)	Grade	Low Grade	High Grade
Hemoglobin (g/L)	Grade 4	<1.7	
	Grade 0	≥LLN	≤ULN
	Grade 1	[100; LLN[]ULN; ULN + 20]
	Grade 2	[80; 100[]ULN + 20; ULN + 40]
	Grade 3	<80	>ULN + 40
INR	Grade 0		If not on anticoagulant or baseline not available: ≤1.2 If on anticoagulant and baseline available: ≤baseline
	Grade 1		If not on anticoagulant or baseline not available:]1.2; 1.5] If on anticoagulant and baseline available:]baseline; 1.5*baseline]
	Grade 2		If not on anticoagulant or baseline not available:]1.5; 2.5] If on anticoagulant and baseline available:]1.5*baseline; 2.5*baseline]
	Grade 3		If not on anticoagulant or baseline not available: >2.5 If on anticoagulant and baseline available: >2.5*baseline
Ionized calcium (mmol/L)	Grade 0	≥LLN	≤ULN
	Grade 1	[1.0; LLN[]ULN; 1.5]
	Grade 2	[0.9; 1.0[]1.5; 1.6]
	Grade 3	[0.8; 0.9[]1.6; 1.8]
	Grade 4	<0.9	>1.8
Lymphocytes (G/L)	Grade 0	≥LLN	≤4
	Grade 1	[0.8; LLN[
	Grade 2	[0.5; 0.8[]4.0; 20.0]
	Grade 3	[0.2; 0.5[>20
	Grade 4	<0.2	
Magnesium (mmol/L)	Grade 0	≥LLN	≤ULN
	Grade 1	[0.5; LLN[]ULN; 1.23]
	Grade 2	[0.4; 0.5[
	Grade 3	[0.3; 0.4[]1.23; 3.30]
	Grade 4	<0.3	>3.30
Neutrophils (G/L)	Grade 0	≥LLN	
	Grade 1	[1.5; LLN[
	Grade 2	[1.0; 1.5[
	Grade 3	[0.5; 1.0[
	Grade 4	<0.5	
Platelets (G/L)	Grade 0	≥LLN	
	Grade 1	[75; LLN[
	Grade 2	[50; 75[
	Grade 3	[25; 50[
	Grade 4	<25	
Potassium (mmol/L)	Grade 0	≥LLN	≤ULN
	Grade 1]ULN; 5.5]
	Grade 2	[3.0; LLN[]5.5; 6]
	Grade 3	[2.5; 3.0[]6; 7]
	Grade 4	<2.5	>7

CL1-95031-006 - Statistical Analysis Plan | VV-TMF-222226 | 1.0

S 095031

CL1-95031-006 - Statistical Analysis Plan - Final version 1.0

Parameter (unit)	Grade	Low Grade	High Grade
Serum creatinine (umol/L)	Grade 0		\leq ULN
	Grade 1] \leq ULN; 1.5*ULN]
	Grade 2		If baseline available:]1.5*baseline; 3.0*baseline] If baseline not available:]1.5*ULN; 3.0*ULN]
	Grade 3		If baseline available:]3.0*baseline; 6.0*baseline] If baseline not available:]3.0*ULN; 6.0*ULN]
	Grade 4		$>$ 6.0*ULN
Sodium (mmol/L)	Grade 0	\geq LLN	\leq ULN
	Grade 1] \geq LLN; LLN[] \leq ULN; 150]
	Grade 2] \geq 150; 155]
	Grade 3] \geq 120; 130[] \geq 155; 160]
	Grade 4	$<$ 120	$>$ 160
Total bilirubin (umol/L)	Grade 0		If baseline value normal or not available: \leq ULN If baseline value abnormal or post-baseline: \leq baseline
	Grade 1		If baseline value normal or not available:] \leq ULN; 1.5*ULN] If baseline value abnormal or post-baseline:]baseline; 1.5*baseline]
	Grade 2		If baseline value normal or not available:]1.5*ULN; 3.0*ULN] If baseline value abnormal or post-baseline:]1.5*baseline; 3.0*baseline]
	Grade 3		If baseline value normal or not available:]3.0*ULN; 10.0*ULN] If baseline value abnormal or post-baseline:]3.0*baseline; 10.0*baseline]
	Grade 4		If baseline value normal or not available: $>$ 10.0*ULN If baseline value abnormal or post-baseline: $>$ 10.0*baseline
WBC (G/L)	Grade 0	\geq LLN	\leq 100
	Grade 1] \geq LLN; LLN[
	Grade 2] \geq LLN; 3.0[
	Grade 3] \geq LLN; 2.0[$>$ 100
	Grade 4	$<$ 1.0

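### SAP Appendix A, as printed, gives toxicity grades to some in-range liver values and no grade to some raised creatinine values

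*SAP*

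**What the plan says.** SAP 5.4.3 assigns grades to CTCAE-covered tests through Appendix A. In Table (A) 1 each liver row gives two lines per grade. One is in multiples of ULN, for a baseline that is normal or missing. The other is in multiples of baseline, and its condition differs between rows:

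- **ALT, AST and total bilirubin (Grades 0 to 4) and GGT (Grades 0 to 3)** use *or*. ALT Grade 1: "If baseline value abnormal or post-baseline: [1.5*baseline; 3.0*baseline". Bilirubin Grade 1: "If baseline value abnormal or post-baseline:]baseline; 1.5*baseline". GGT Grade 1: "If baseline value abnormal or post-baseline:]2.0*baseline; 2.5*baseline".
- **ALP** has the same layout with *and*: "If baseline value abnormal and post-baseline: <2.0*baseline".
- **GGT Grade 4** does not mention post-baseline: "If baseline value abnormal: >20.0*baseline".
- **Glucose, high side, Grade 0** uses the baseline only when it is raised: "If baseline available and >ULN: ≤baseline". The row between corrected calcium and GGT, whose label is lost in the available text, requires both conditions for Grade 1: ">ULN and If post-baseline: >baseline".

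For ties the appendix says: "In case there are several grades for the same record, choose the worst grade (i.e., grade with the highest number".

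For serum creatinine with a baseline available, Grades 0, 1 and 4 are bounded by ULN, and Grades 2 and 3 by baseline.

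SAP 4.2 takes baseline as the last observation before the first dose. Protocol 10.1.6.2.2 gives Grade 0 to any non-missing value that is not graded 1 or higher. SAP 5.4.3 does not repeat that default.

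**The concern.** With *or*, the baseline line applies to every on-study record, including those of participants whose baseline was normal. Such a record satisfies two lines, and the worst-grade rule keeps the higher. The baseline line can therefore add a grade but never remove one, and it overrides the same row's own statement that a value at or below ULN is Grade 0. The term *abnormal* is not defined either, so it could take in a baseline below LLN.

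For creatinine, mixing two reference points leaves intervals that belong to no grade. Under the protocol default those values would be listed as Grade 0, although the SAP's own Grade 0 stops at ULN.

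A reader of the listings could thus see Grade 1 to 3 against an in-range liver test, and Grade 0 or a blank against creatinine more than six times its baseline. SAP section 5 generally drops tables and figures, so the listings are the main laboratory output and nothing else corrects them.

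**Working it through.** The plan gives no figure to reproduce. The check applies the printed bands literally and then takes the worst grade. The documents state no ULNs, so these are assumptions: ALT/AST 40, bilirubin 21, GGT 50, creatinine 100 µmol/L. Only ratios to ULN and to baseline matter.

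**Liver rows, normal baseline, post-baseline record.** Compare value/ULN with the ULN line and value/baseline with the baseline line.

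| Test | Baseline to value | Value/baseline | ULN line | Baseline line | Grade as written |
|---|---|---|---|---|---|
| ALT | 30 to 38 | 1.27 | 0 | 0 | 0 |
| ALT | 20 to 35 | 1.75 | 0 | 1 | 1 |
| ALT | 10 to 35 | 3.5 | 0 | 2 | 2 |
| Bilirubin | 10 to 11 | 1.1 | 0 | 1 | 1 |
| Bilirubin | 10 to 16 | 1.6 | 0 | 2 | 2 |
| Bilirubin | 5 to 16 | 3.2 | 0 | 3 | 3 |

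For any ULN:

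- In-range ALT or AST can reach Grade 1 when 1.5 × baseline ≤ ULN, that is, baseline up to about 0.67 × ULN.
- In-range bilirubin is graded after any rise from a baseline below ULN.
- In-range Grade 3 for ALT, AST or GGT needs 5 × baseline < ULN, that is, baseline below 0.20 × ULN.
- For a baseline above ULN, *or* and *and* give the same post-baseline grade.

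All integer pairs with a normal baseline and values up to 30 × ULN were also enumerated. The baseline line raised the ALT grade in 19,873 of 48,000 pairs and lowered it in none. Among in-range pairs, 533 of 1,600 for ALT and 210 of 441 for bilirubin were graded above 0. These count combinations. They are not expected frequencies.

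**Undefined abnormality.** With an assumed ALT LLN of 7, a baseline of 5 could count as abnormal. A value of 30 is then 30/5 = 6 × baseline, Grade 3 on the baseline line alone.

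**Creatinine, baseline available.** There are two gaps:

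- Baseline above ULN: Grade 1 ends at 1.5 × ULN and Grade 2 starts above 1.5 × baseline.
- Baseline below ULN: Grade 3 ends at 6 × baseline and Grade 4 starts above 6 × ULN.

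| Baseline | Values with no grade |
|---|---|
| 50 | 301–600 |
| 60 | 361–600 |
| 80 | 481–600 |
| 100 | none |
| 110 | 151–165 |
| 130 | 151–195 |
| 150 | 151–225 |

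Raised baselines are eligible, because inclusion criterion 12 caps creatinine clearance and not serum creatinine. For a 50-year-old, 80 kg man at 50 mL/min, (140 − 50) × 80 / (72 × 50) = 2.0 mg/dL, about 177 µmol/L.

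**Single cells.**

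- GGT Grade 4 as printed makes the grade fall as the value rises when a normal baseline is below 0.25 × ULN. At baseline 10, a value of 200 is 20 × baseline, Grade 3. A value of 201 leaves the baseline bands and is 201/50 = 4.02 × ULN, Grade 2.
- GGT at exactly 2.0 × a raised baseline is in neither Grade 0 (below 2.0) nor Grade 1 (above 2.0).
- Ionized calcium low Grade 4 (below 0.9) overlaps Grade 3 (0.8 up to 0.9).

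**The case against.** The strongest reply is that the two lines were meant as alternatives, as in ALP, or that the phrase means a post-baseline value that is itself abnormal. Under the first reading the *or* is a slip, and a programmer might code it correctly anyway. Under the second, in-range values escape, but raised values are still over-graded: ALT from 10 to 60 is 6 × baseline, Grade 3, against 60/40 = 1.5 × ULN, Grade 1. Neither reading is what the text says, and the worst-grade rule points the other way.

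A second objection is that the CTCAE text is not in the documents, so no external standard shows which row is wrong. That stands. The case rests on internal evidence: the Grade 0 line at or below ULN, the ALP, glucose and unlabelled rows, and creatinine intervals that no band covers.

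Third, the extracted table is visibly damaged, and the creatinine Grade 1 cell is among the affected cells. Damage does not explain an *or* repeated across four rows, and the creatinine Grade 2 to 4 limits are legible. They should still be checked against the source along with the rest. The GGT bracket and ionized calcium points are weaker. Ionized calcium is in neither the protocol's chemistry panel nor SAP Table (5.4.3) 1, so it may never be used.

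Finally, the practical effect is small. That is accepted and sets the severity.

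**Conclusion.** The point holds as a minor error in the SAP as written. Four liver rows can grade in-range values, up to Grade 3 in the examples, and creatinine has ungraded intervals at every baseline other than ULN itself. The worked values rest on assumed ULNs, but the ratio thresholds do not.

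How often this would occur is unknown. The documents give no baseline values, and Protocol 2.1.1 lists abnormal liver tests among common presenting features, so some participants will have raised baselines, where the *or* wording makes no difference.

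The reach is the grades in the laboratory listings of the 7 enrolled participants. Raw values are still listed. DLT grading rests on Investigator assessment (Protocol 4.1.4.2) and SAP 5.4.1.2 does not derive TEAE severity from Appendix A, so no DLT, RCD or TEAE result changes.

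**What to change.** **ALT, AST, GGT (all grades), bilirubin and ALP.** Use the ULN line when baseline is at or below ULN or missing, and for all pre-dose records. Use the baseline line only when baseline is above ULN and the record is post-baseline. This replaces the undefined *abnormal*. ALP is included because its present wording gives a raised baseline record no rule at all. Start GGT Grade 1 at 2.0 × baseline inclusive so that it meets Grade 0. When this repair was run on the ALT, AST, bilirubin and GGT rows, no value was left ungraded, grades never fell as values rose, and every in-range value with a normal baseline was Grade 0.

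**Creatinine.** Close both gaps in one of two ways:

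- *Option A:* Grade 2 if above 1.5 and up to 3.0 × baseline or × ULN. Grade 3 if above 3.0 × baseline, or above 3.0 and up to 6.0 × ULN. Grade 4 if above 6.0 × ULN. Take the worst grade. This moves some existing grades when baseline is raised (baseline 130: 301–390 goes from 2 to 3). It also keeps in-range grading on baseline multiples (50 to 80 stays Grade 2), which the SAP should state.
- *Option B:* Grade 1 for any value above ULN not graded higher, and Grade 3 if above 3.0 × baseline. This changes no existing grade.

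Both leave no gap and are monotone at the 11 baselines tested from 50 to 150.

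Check the GGT Grade 4 clause, the ionized calcium low Grade 4 limit and the creatinine cells against the source. The cost is a few lines in Appendix A and the grading program, with no new data.
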